### Sample Size and Population

The target population is male and female youth between the ages of 11-16 with functional abdominal pain disorders (FAPD) and clinically significant anxiety. Youth will be recruited from pediatric gastroenterology clinics at Helen DeVos Children's Hospital. We aim to have between 17 – 25 participants in each arm for a total N of 34 - 50 participants in the study. Gender and age will be used as blocking variables in randomization.

## 1. STUDY OBJECTIVES

### 1.1 Primary Objective

Left AMY-PFC functional connectivity will be *significantly* reduced (i.e., decreased hyperconnectivity) post ADAPT vs. waitlist.

### 1.2 Secondary Objectives

Brain activations associated with cognitive (PFC), affective (pgACC, AMY), and visceral afferent (INS, thalamus, aMCC, S1 & S2) pain will be significantly more diminished after ADAPT vs. waitlist.

*Exploratory Aim.* Changes in functional connectivity and brain activations following ADAPT will correspond to reductions in pain (intensity and unpleasantness) and anxiety ratings.

## 2. BACKGROUND AND RATIONALE

### 2.1 Background on Condition, Disease, or Other Primary Study Focus

Functional abdominal pain disorders (FAPD) are the most common chronic pain conditions of childhood and are associated with significant functional disability. FAPD impacts >10% of youth in community samples and accounts for up to 50% of gastroenterology (GI) visits. FAPD is associated with significant functional impairment, including psychological problems, such as anxiety and depression. Youth with FAPD are more prone to social and academic difficulties, including school refusal/absences, poor academic performance, and social problems. Impairment and disability are likely to persist, with 25%-45% affected after 5 years. Increased healthcare utilization and medical costs are substantial and include invasive and unnecessary medical procedures, such as blood work-up (92%), endoscopic studies (51%), and abdominal x-rays (39%). Such work-ups are common, costly (\$6,104 per patient), and are associated with medical complications. Although the total cost of pediatric FAPD is unknown, the cost in adults is estimated to be \$20 billion a year. Given that a substantial proportion of youth continue to experience symptoms over time and may even develop other chronic pain conditions, the total cost of pediatric FAPD is likely substantial. Early and effective intervention may play a key role in preventing long-term problems.

Anxiety is highly prevalent and predicts poor outcomes. A large proportion of youth with FAPD meet criteria for a concurrent anxiety disorder. Anxiety disorders are characterized by extreme distress and worry and may be generalized or result from specific triggers, such as separation from attachment figures or social situations. In youth with FAPD presenting to GI clinics, anxiety disorders are estimated to affect 42% to 85%. Further, prior research has found that *clinically significant anxiety* is common and predicts increased functional impairment. Clearly, youth with FAPD *and* clinical anxiety are the most common and most clinically complicated manifestation of FAPD.

Conventional treatments are ineffective for many youth with FAPD. Pharmacologic treatments (i.e., antispasmodic agents, low-dose psychotropics) for FAPD have limited evidence and efficacy. Cognitive behavioral therapy (CBT) for pain is a conventional non-pharmacologic treatment that uses cognitive strategies (e.g., reducing catastrophic thinking about pain) and behavioral approaches (e.g., activity pacing, behavioral activation) to improve functioning and reduce pain symptoms in youth with chronic pain such as FAPD. However, a substantial proportion (~40%) fail to respond and the presence of elevated anxiety can attenuate response to pain-focused CBT. Including specific treatment components to manage clinical anxiety is the next logical step for these patients.

Mindfulness may amplify the efficacy of conventional treatments. Mindfulness includes attending to experiences in the present moment and using a nonjudgmental attitude, and is effective for managing pain and anxiety. Pain reduction following mindfulness in healthy adults has been shown to be related to changes in activation of the primary sensory cortex (S1), insula (INS), anterior cingulate cortex (ACC), and prefrontal cortex (PFC) brain regions. Moreover, improvements in anxiety following mindfulness are characterized by enhanced PFC connectivity with the amygdala (AMY) during resting state and changes in the ACC, PFC, and INS in healthy adults.

In general, the neurobiological underpinnings of visceral pain in FAPD are poorly understood although anxiety is likely to play a crucial role in understanding psychological treatment response for pain. Research suggests pain is experienced through the pain connectome, a whole-brain-wide network that integrates cognitive, affective, and sensorimotor aspects. Recent reviews of prior neuroimaging studies in IBS, the most common subtype of FAPD, suggest that common areas of activation in response to pain include regions associated with visceral afferent processing, such as the thalamus, INS, anterior midcingulate cortex (amCC), and the primary and secondary sensory cortices (S1 & S2). Interestingly, brain regions associated with emotional arousal, including the pregenual anterior cingulate cortex (pgACC) and AMY, are also activated by pain induction in FAPD, but not in healthy controls. In adolescents with FAPD (IBS), structural abnormalities were observed in the INS and S1, in addition to structural and functional abnormalities in the PFC, and posterior cingulate (PCC). Although brain regions associated with anxiety may play an important role in the expression of pain (i.e., FAPD), there is limited hypothesis-driven research examining the role of anxiety. Anxiety alone is associated with AMY hyperactivations and PFC hypoactivations.

Neural mechanisms may offer insights on response to a tailored intervention for youth with FAPD. There have only been two research studies examining neural mechanisms of treatment response to non-pharmacologic interventions for FAPD (in adults with IBS). However, these studies use an invasive and potentially risky pain induction technique (rectal distention), though less invasive methods (such as water loading) to induce visceral pain are available. The first found that improvements in pain using cognitive therapy were associated with reduced rectal distention-induced activations in the AMY and the pgACC. However, functional connectivity analysis was not undertaken. The second compared hypnotherapy for pain to an educational control and found that the brain response to rectal distension after treatment was

similar to that observed in HCs, suggesting that the treatment had a normalizing effect on the central processing abnormality of visceral pain signals in IBS. Hypnosis responders demonstrated a BOLD attenuation in posterior INS while education responders had a BOLD attenuation in prefrontal cortex. Moreover, in a pediatric pain sample, a positive response to an intensive integrated treatment for complex regional pain syndrome was related to a reduced hyperconnectivity between the IAMY and regions including the PFC; but research specific to pediatric FAPD is needed. [name] pilot study has shown IAMY-PFC changes in functional connectivity following a symptom provocation task. Further, CBT for pediatric pain (migraine) alters interactions between affective regions (AMY) and structures involved in cognitively driven pain modulation (PFC). Thus, the AMY might represent an important mechanism linking anxiety to sensory processing mechanisms.

These findings suggest that complex neuromechanistic processes account for response to psychological interventions. However, there is no research to our knowledge that distills the mechanism of the effect in a psychological intervention for youth with FAPD and comorbid anxiety. It is plausible that a psychological intervention tailored to anxiety and pain symptoms in FAPD would impact neuromechanisms that link cognitive and visceral afferent processing with emotional arousal (i.e., IAMY-PFC connectivity). Determining such information is critical for identifying brain mechanisms of effective treatments. For example, if IAMY-PFC connectivity is significantly altered following ADAPT (e.g., reduced hyperconnectivity), this evidence would offer further support for the importance of targeting anxiety and pain in youth with FAPD.

## 2.2 Study Rationale

Given this research evidence, Aim to Decrease Pain and Anxiety Treatment (ADAPT) was developed. ADAPT is a cognitive behavioral approach to manage pain and anxiety for youth with FAPD and comorbid anxiety. For the current study, ADAPT is enhanced with mindfulness meditation. Thus, ADAPT focuses on decreasing attention to pain and anxiety using conventional strategies (CBT), as well as training in mindfulness meditation techniques, such as mindful breathing, developing a mindful awareness of bodily sensations, recognizing the impact of stress on functioning. ADAPT utilizes a blend of 2 interactive sessions with a psychological provider (1 hour, via videoconference) and 4 web-based, self-paced modules (45 minutes) with therapist support videoconferencing and/or phone calls (15 minutes). The Zoom-based ADAPT sessions will be video-recorded. The ADAPT intervention period is approximately 6 weeks (up to eight weeks will be allowed for scheduling flexibility). Based on our prior research, there are no known risks associated with the ADAPT intervention.

## 3. STUDY DESIGN

- **Type/design of trial:** Masked clinical trial
- **Specific statement of the primary and secondary outcomes:** The primary outcome is that left AMY-PFC functional connectivity will be significantly reduced (i.e., decreased

hyperconnectivity) post ADAPT vs. waitlist. The secondary outcome is that brain activations associated with cognitive (PFC), affective (pgACC, AMY), and visceral afferent (INS, thalamus, aMCC, S1 & S2) pain will be significantly more diminished after ADAPT vs. waitlist. We will also explore whether changes in functional connectivity and brain activations following ADAPT correspond to reductions in pain (intensity and unpleasantness) and anxiety ratings.

- **Study population and groups/arms including sample size:** The target population is male and female youth between the ages of 11-16 with functional abdominal pain disorders (FAPD) and clinically significant anxiety. Youth will be recruited from pediatric gastroenterology clinics at Helen DeVos Children's Hospital. We aim to have between 17 – 25 participants in each arm for a total N of 34 - 50 participants in the study. Gender and age will be used as blocking variables in randomization.
- **Study location:** The study is located Helen DeVos Children's Hospital/Spectrum Health.
- **Approximate duration of enrollment period and follow-up:** Participants will be recruited from GI clinics and enrolled in the study during that visit (immediately). They will then come in for the baseline assessment, which will occur approximately one week after enrollment (though up to six weeks after enrollment will be allowed to account for MRI scanner availability). Following that visit, they will then be randomized to either the ADAPT group or a waitlist control group (each six weeks in duration) and will be informed of group assignment within a week of their baseline assessment, and will begin ADAPT/waitlist approximately one week after group assignment (with up to three weeks allowed to begin ADAPT). Up to eight weeks will be permitted for the six ADAPT sessions to account for potential scheduling conflicts and participant illness. Upon completion of ADAPT or waitlist control, participant outcomes will be reassessed at the post assessment visits (approximately six weeks after ADAPT/waitlist). After completing the post assessment visit, participants in the waitlist control group will be given the opportunity to complete ADAPT.

Participants randomized to ADAPT will be actively involved in the study for a ~10 week period (from screening to post assessment). Those who are randomized to the waitlist control and then opt to receive ADAPT afterwards will be involved for ~16 weeks.

It is anticipated that we will be actively enrolling participants for 2 years. After study completion, three additional months will be allotted for data analysis.

- **Description of intervention and administration.** In this study, a psychological intervention, Aim to Decrease Anxiety and Pain Treatment (ADAPT), was developed and will integrate mindfulness meditation with cognitive behavioral therapy approaches for managing pain and anxiety to improve patient outcomes. ADAPT is an individual therapy with caregiver involvement that consists of 2 interactive sessions with a psychological provider (60 minutes) once per week for the first two weeks, followed by 4 weeks of self-paced web modules (45 minutes per week) in conjunction with interventionist support (15 minutes per week). Participants will complete the ADAPT program virtually (e.g., using HIPPA compliant videoconferencing or phone). The duration of ADAPT is 6 weeks, although up to eight weeks will be permitted to account for scheduling conflicts and participant illness. Preliminary testing has shown that ADAPT successfully reduces pain and anxiety over time.

Participants randomized to ADAPT will be actively involved in the study for a ~10 week period (from screening to post assessment). Those who are randomized to the waitlist control and then opt to receive ADAPT afterwards will be involved for ~16 weeks.

- **Randomization, blinding:** Participants will then be randomized to either ADAPT or waitlist control. Gender and age will be used as blocking variables in randomization. For further detail on randomization, see 9.2 *Sample Size and Randomization*. The PI ([name]), data analyst ([name]), and outcome assessors (post-baccalaureate research coordinator) will be blinded to intervention group assignment. The study statistician ([name]), PI ([name]), and mentorship team ([name] and [name]) will be blinded to the primary mechanistic outcome measure. For further detail on blinding, see 6.2.3 *Blinding*.
- **Other protocol specific details:** Participants with FAPD will be recruited from gastroenterology clinics. We will work with [name] [name] (who already provides outpatient clinical/psychological care for patients in the GI clinics) to identify potentially appropriate patients. Of note, the GI section chair, [name] is supportive of the project and has agreed to facilitate clinical recruitment and consultation efforts for the study. [name], along with the other GI physicians of the section, are close collaborators of [name] [name]. With [name] [name]'s established relationships within GI, we will be able to work broadly with members of the GI team at HDVCH.

Potentially appropriate participants will be contacted by a member of the medical team and/or by a study staff member. They will be described the study in detail and participants will have the opportunity to ask questions and voice concerns. If the patient/family is agreeable, informed consent/assent will be obtained and participants will be screened for study eligibility. Qualifying patients will then be scheduled to complete the baseline assessment visit (clinical measures/WL-SPT with fMRI). After this visit, participants will be randomized to either the ADAPT treatment group or a waitlist control (each condition will last for approximately 6 weeks). The post assessment will be similar in format to the baseline assessment. Those randomized to waitlist will be eligible to receive ADAPT after the post assessment.

#### 4. SELECTION AND ENROLLMENT OF PARTICIPANTS

The study population is male and female youth between the ages of 11-16 diagnosed with functional abdominal pain disorders (FAPD) and clinically significant anxiety. We plan to approach approximately 124 participants, ages 11-16 years. Of those, we expect 75% will agree to participate (n=93) based on our pilot fMRI study. Of those, we expect approximately 65% will qualify. Thus, we anticipate recruiting n=60 to complete a baseline assessment. Based on our previously RCT, we expect 85% of those recruited in clinic will complete the baseline assessment (n = 50) and the majority will be retained in the study (90%, n=45). Based on our fMRI pilot study, we expect to lose approximately 10% of participant data to movement artifacts yielding n=40 with usable data. The minimum number of total completed participants allowed will be 34 and the maximum will be 50.

We will recruit males and females to participate in this study. While FAPD is more common in females, we have found that we are easily able to recruit males as well. Based on our prior research projects, we expect that we will recruit a sample of youth with FAPD that is 65% female and 35% male. The PI ([name]) will check in with the mentorship team ([name] and [name]) quarterly regarding enrollment and gender breakdown in a blinded fashion. If the gender breakdown is skewed (>85% females or >60% males), the PI ([name]) will problem solve with study mentors ([name] and [name]) to ensure the sample is representative of the

population. Recruitment efforts would target candidates from underrepresented gender until the sample is more representative of the FAPD population.

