## 9.2 Sample Size and Randomization

We've used the following tool (<http://neuropowertools.org/neuropower/neuropowerinput/>) to conduct sample size calculations for the fMRI portion of the study. Power calculations were based on prior studies conducted by the PI's previous study mentor, who collected functional connectivity data 1) pre and post psychological therapy for pediatric pain (migraine), and 2) comparing individuals with pediatric pain (migraine) to healthy controls. While these groups are not synonymous with those proposed in the current study (which aims to compare youth with FAPD who have received psychological therapy for pain and anxiety to those in a waitlist control condition), this preliminary data yields meaningful information by which we can estimate the power required for the proposed investigation. The power calculations and sample size requirements are detailed below:

*For within group changes*, we relied on the pre/post data following a psychological therapy for pediatric pain (migraine). Here we found that a total sample size of 34 would be required for power of .8 and  $p < 0.05$ . *For between group changes*, we utilized data comparing youth with chronic pain (migraine) to healthy controls. Based on these data, a total of 35 subjects are required for power of .8 and  $p < 0.05$ . All comparisons were calculated using z-transformed statistical images of the whole brain, a cluster-forming threshold of  $z > 3.1$  and  $p < 0.05$ , and a Gaussian Random Field theory-based approach for multiple comparisons. For these complex data, statistical power is defined as an 80% probability of correctly detecting an active peak for all peaks above the cluster-forming threshold. We note moderate to large effects observed for within and between group studies; thus, a total sample size of 40 ensures we are adequately powered to observe at least moderate (e.g. mean effect size difference of 0.4 or greater) effects.

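### The permitted minimum of 34 completers sits below the plan's own between-group requirement of 35 and, read plainly, is counted before the expected scan loss

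*Combined protocol and SAP*

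**What the plan says.** Section 1.1 makes the primary objective a comparison of ADAPT with waitlist on left amygdala-prefrontal connectivity.

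Section 9.2 gives two sample sizes from a web-based peak-power tool. For change within a group: "Here we found that a total sample size of 34 would be required for power of .8". For differences between groups: "a total of 35 subjects are required for power of .8". It then states that "a total sample size of 40 ensures we are adequately powered to observe at least moderate" effects, and gives 0.4 as an example without naming the effect-size metric.

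Section 4 sets out a recruitment funnel that ends with 45 children retained and then a separate step: "we expect to lose approximately 10% of participant data to movement artifacts yielding n=40 with usable data". The next sentence sets the limits: "The minimum number of total completed participants allowed will be 34 and the maximum will be 50". The Précis gives the same range as "between 17 – 25 participants in each arm for a total N of 34 - 50 participants", and section 3 repeats it.

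Section 9.3 defines the analysis population by completion of an assessment after randomization and does not mention scan quality.

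**The concern.** The lowest size the plan accepts does not reach the size the plan itself requires for its primary comparison. Two things contribute. The floor of 34 is one below the between-group figure of 35. It is also expressed in children who complete, whereas the primary outcome needs usable imaging, and section 4 treats these as different counts (45 and 40).

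Section 9.4 names slow accrual and high losses to follow-up as possible problems, so the trial could end near its floor. It would then have met its stated minimum while falling short of the 0.8 power on which section 9.2 bases its sample size, and the documents do not tell a reader of a null primary result by how much.

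**Working it through.** **1. Inputs.** Floor 34 and ceiling 50 completers (section 4); 17 to 25 per arm (Précis, section 3); between-group requirement 35 at power 0.8 and p < 0.05, sidedness not stated, cluster-forming threshold z > 3.1 (section 9.2); retention 90% and movement loss about 10% (section 4).

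**2. The plan's own figures.** The funnel in section 4 reproduces up to rounding: 124 x 0.75 = 93; 93 x 0.65 = 60.45 (stated 60); 60 x 0.85 = 51 (stated 50); 50 x 0.90 = 45; 45 x 0.90 = 40.5 (stated 40). The 35 and 34 cannot be reproduced. They come from pilot statistical maps (children with migraine before and after therapy, and against healthy controls), and the peak effects are not given. I therefore take 35 as giving exactly 0.80.

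**3. Usable scans at the floor.** 34 x 0.9 = 30.6, about 31, which is four to five short of 35.

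**4. Power at the floor.** For a simple two-group contrast with equal arms, the signal grows with the square root of the total N. With power fixed at 0.80 for N = 35,

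power(N) = Phi[(z_a + 0.842) x sqrt(N/35) - z_a].

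- Two-sided 0.05, N = 34: 2.802 x 0.986 - 1.960 = 0.802, so power is 0.789.
- Two-sided 0.05, N = 30.6: 2.802 x 0.935 - 1.960 = 0.660, so power is 0.745.
- Threshold z > 3.1, N = 30.6: 3.942 x 0.935 - 3.1 = 0.586, so power is 0.721.

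The same calibration with the noncentral t distribution is the second figure in each cell:

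| Threshold | 40 usable | 34 usable | 30.6 usable |
|---|---|---|---|
| 0.05 two-sided | 0.850 / 0.852 | 0.789 / 0.788 | 0.745 / 0.741 |
| 0.05 one-sided | 0.845 / 0.846 | 0.790 / 0.789 | 0.752 / 0.749 |
| z > 3.1, one-sided | 0.867 / 0.876 | 0.784 / 0.781 | 0.721 / 0.706 |

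**5. Floor needed before scan loss.** 35 / 0.9 = 38.9, so 39 completers (39 x 0.9 = 35.1; 38 x 0.9 = 34.2 is too few). The funnel expects 45.

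**6. The 0.4 effect at a total of 40.** If 0.4 is a standardized mean difference in a simple two-sample comparison with 20 per arm, z = 0.4 x sqrt(20/2) = 1.265. Power is Phi(1.265 - 1.960) = 0.24 two-sided or Phi(1.265 - 1.645) = 0.35 one-sided, and 0.8 would need 198 or 156 children in total. If 0.4 is instead Cohen's f, which corresponds to a difference of 0.8 SD, 20 per arm gives 0.69 two-sided and about 0.80 one-sided. The documents do not say which is meant.

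**The case against.** The strongest reply is that the planned design is sound on its own terms. Section 9.2 ties adequacy to 40, the funnel delivers 40 usable scans, and power there is about 0.85 or a little more on the same scaling. A reader might infer that the trial as planned is underpowered against its own requirement. The documents do not support that: only the contingency minimum falls short.

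Second, the scan-loss reading is an inference. Completion is not defined, the floor sentence directly follows the count of usable scans, and the ceiling of 50 equals the number expected at baseline, before any attrition, so the term is used loosely. This stands as a limit. Even so, section 4 counts retained children and usable data as separate steps, the Précis and section 3 count participants, and nothing says the 34 are usable scans.

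Third, the gap between 34 and 35 is trivial by itself, at one to two points of power. That is right.

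A reader might also infer that the within-group 34 was mistakenly used as the floor, or that a null result at 34 would be reported as having 80% power. The numbers coincide, but the documents do not say where the floor came from. Nor do they say how a null result would be described, and section 9.4 allows slow accrual or high losses to go to review with the mentors, the monitoring committee and the funder.

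Finally, a reader might conclude that power for the 0.4 effect is only about 0.24. That holds only for one reading of an unspecified metric, in a simple test that is not the mixed-effects analysis of section 9.6.

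**Conclusion.** The concern holds for the floor. The permitted minimum is below the between-group requirement. On the plain reading it leaves about 31 usable scans against 35 and power of roughly 0.71 to 0.75 instead of 0.80. If the floor was meant as usable scans, the shortfall is one child and about 0.79.

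These powers assume that 35 gives exactly 0.80, that the contrast is a simple two-group one with equal arms, and that movement loss is 10%. The plan's power is defined per peak above a cluster threshold, so they show the order of the loss and are not a re-run of the tool. This is a modest correction to a stated limit and leaves the planned target intact.

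The 0.4 statement is a separate gap in reporting. It cannot be judged until the metric is given. As a standardized mean difference in a simple two-sample comparison, it would not be detectable with 0.8 power at 20 per arm.

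**What to change.** In sections 4 and 9.2, do one of the following:

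- Define the floor as children with usable scans at both baseline and post assessment, and set it at 35 or more. With 10% loss that is about 39 completers.
- Keep 34 completers and state that between-group power there is below 0.8, roughly 0.7 to 0.75 by scaling from 35, with the approximation noted.

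Either way, say what counts as completed, and restate the 17-per-arm minimum in the Précis and section 3 on the same basis. A total of 35 means 17 and 18 per arm. If equal arms are wanted, 18 per arm needs 36 / 0.9 = 40 completers.

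In section 9.2, name the metric behind 0.4 and the test it refers to, or remove the sentence.

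The second option costs only wording and a less favourable stated power. The first also raises a feasibility limit by about five completers, but the 45 completers already expected exceed it, so planned enrolment does not change.
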